#### **6.5.4 *Multicenter Studies***

The trial will be conducted in up to 25 clinical centers. Data will be pooled across all clinical centers. A sensitivity analysis of the primary endpoint will be conducted using a mixed effect log-binomial regression model with center as a random effect.

#### **6.5.5 *Assessment of Balance of the Randomization***

The success of the randomization procedure in balancing important covariates between randomization groups will be assessed. Continuous measures will be compared using t-tests, while chi-square tests will be used to compare categorical variables. Should the treatment groups differ significantly with respect to any covariate at the 0.01 level, we will adjust for those covariates in a secondary analysis of the primary endpoint using multivariable log-binomial regression.

#### **6.5.6 *Examination of Subgroups***

Subgroup analyses of the primary endpoint will be performed for key clinical subgroups, classified at baseline. Pre-defined subgroups include:

- Aneurysm status (recently ruptured (within 15 days) vs. not recently ruptured)
- Dome to neck ratio (not wide neck vs. wide neck)
- Aneurysm location (anterior vs posterior circulation)
- Age (<65, vs. ≥65)
- Sex (male vs. female)
- Race (American Indian or Alaska Native, Asian, Black or African American, Native Hawaiian or Other Pacific Island, and White)
- Ethnicity (Hispanic vs. non-Hispanic)
- Presence of co-morbidities
  - Diabetes (yes vs. no)
  - Obesity (BMI ≥ 30 vs. BMI <30)
  - Smoking status (current, previous (>6 months), never)
- Aneurysm shape (regular vs. irregular/multilobulated)

With the exception of severity of aneurysm status and wide neck status, for which formal interaction terms will be tested, these analyses will be descriptive and conducted to explore the effect of the treatment within the subgroups. Risk ratios with their respective 95% confidence intervals will be reported within each strata. Strata that contain less than 20% of the sample size and/or in which the number of patients assigned to a specific group is less than 20 will not be considered.

## **6.6 Analyses of Secondary Clinical Endpoints**

All secondary clinical endpoints will be analyzed using the ITT population.

### **6.6.1 *Neurologic Morbidity***

The number and percentage of patients who experience neurologic morbidity at 24-hours post-operation will be reported by randomization group. The proportion of patients with neurologic morbidity will be compared between groups using a log binomial model and differences between the groups will be summarized using relative risk and the corresponding 95% confidence interval.

Patients that die within 24-hours will be counted as having neurologic morbidity. Survivors missing the 24-hour NIHSS assessment will have their neurologic morbidity outcome imputed via multiple imputation assuming that the data are missing at random. The imputation model will be stratified by randomization assignment and include age, sex, randomization strata for wide neck status, randomization strata for aneurysm status, aneurysm size, and baseline NIHSS. Since this model includes a mixture of variables types (i.e. continuous and binary), a fully conditional specification method will be used (Berglund 2014). Thirty datasets will be imputed and Rubin's methods will be used to combine them and estimate treatment effect (Rubin 1986).

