#### 7.1.3 Reporting

All adverse events must be recorded on the Event eCRF with the following information:

1. Whether it was anticipated
2. Its relationship to the procedure, clinical course of the disease, device, or non-procedure
3. Outcome/Patient status
4. Treatment provided
5. Whether an action was taken and a description of said action

All serious adverse events must also be recorded on the Event eCRF with the following additional information:

6. Type of Serious Adverse Event
7. Whether it was reported within 72 hours of becoming aware of the event
8. Whether it happened during the procedure
9. Background Information
10. Whether it will be reported to the local IRB
11. Territory where initial procedure occurred

12. Whether it was serious (not life threatening), serious (life threatening) or lead to death

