#### 3.1.1 Study Duration and Time Points

All patients will be followed for 12 to 18 months post-procedure. Endpoints will be measured at discharge from the index procedure, 3 to 6 months post-procedure, and 12 to 18 months post-procedure. The 3 to 6 month visit and 12 to 18 month visit align with standard of care visits.

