###### **5.2.1 Morbidity/Mortality**

- Neurologic morbidity measured at 24-hours post-procedure. Morbidity is defined by neurologic worsening measured by a greater than or equal to 4-point change in the NIH Stroke Scale (NIHSS) from pre-surgical baseline.

- Mortality through end of study follow-up (12 to 18 month visit)

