### 6.5.3 *Missing Primary Endpoint Data*

Patients without previous evidence of inadequate angiographic occlusion, either on the 3 to 6 month visit angiogram or on a clinically driven angiogram taken prior to study exit, that miss the 12 to 18 month angiogram, or whose 12 to 18 month angiogram is not readable by the core lab, will be missing the primary endpoint. Patients missing the primary endpoint who die prior to or during the 12 to 18 month visit window (up to 18 months post-randomization) and die with known cause of death related to their aneurysm or unknown cause of death will be considered treatment failures with inadequate occlusion. Patients missing the primary endpoint with a known cause of death unrelated to their aneurysm will be considered missing.

Patients with missing primary endpoint data will have their 12 to 18 month angiographic

occlusion status imputed via multiple imputation assuming that the data are missing at random. The imputation model will be stratified by randomization assignment and include age, sex, randomization strata for aneurysm status, randomization strata for wide neck status, aneurysm size, and angiographic occlusion status at the 3 to 6 month visit. Since this model includes a mixture of variables types (i.e. continuous and binary), a fully conditional specification method will be used (Berglund 2014).

The main feature of the imputation approach is the creation of a set of clinically reasonable imputations for angiographic occlusion for each patient with missing data. This will be accomplished using a set of repeated imputations created by predictive models based on the majority of participants with complete data. The imputation models will reflect uncertainty in the modeling process and inherent variability in patient outcomes, as reflected in the complete data. Thirty datasets will be imputed.

After the imputations are completed, all of the data (complete and imputed) will be combined and the analysis performed for each imputed-and-completed dataset. Rubin's method of multiple (i.e., repeated) imputation will be used to estimate treatment effect (Rubin 1986).

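### The imputation model for missing 24-hour neurologic morbidity (H2) uses only pre-procedure variables and leaves out the discharge NIHSS that the trial already schedules

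*Combined protocol and SAP*

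**What the plan says.** SAP 5.2.1 sets the endpoint at 24 hours after the procedure: "Morbidity is defined by neurologic worsening measured by a greater than or equal to 4-point change in the NIH Stroke Scale (NIHSS) from pre-surgical baseline". SAP 6.6.1 treats early deaths as events ("Patients that die within 24-hours will be counted as having neurologic morbidity") and imputes the rest: "Survivors missing the 24-hour NIHSS assessment will have their neurologic morbidity outcome imputed via multiple imputation assuming that the data are missing at random". The model is stratified by arm, and its covariates are age, sex, the wide-neck stratum, "randomization strata for aneurysm status, aneurysm size, and baseline NIHSS". It uses fully conditional specification and thirty imputations.

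Three other places bear on this.

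- The visit schedule in protocol 6.1 has NIHSS and modified Rankin at discharge. It shows no NIHSS at screening or at the procedure, and has no 24-hour column. SAP 3.1.1 agrees with it: "Endpoints will be measured at discharge from the index procedure, 3 to 6 months post-procedure, and 12 to 18 months post-procedure".
- Protocol 7.1.3 has the event form record, for each serious adverse event, "Whether it happened during the procedure".
- For the primary endpoint, SAP 6.5.3 does use a post-procedure measure of the outcome. Its imputation list ends with "aneurysm size, and angiographic occlusion status at the 3 to 6 month visit".

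In SAP 6.8, H2 is the only hypothesis in family F2. It is tested after H1, and must be rejected before F3 and F4 are tested.

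**The concern.** The outcome is a change caused by, or following, the procedure, yet every predictor in the imputation model predates it. The discharge score is the first post-procedure NIHSS that the protocol schedules. It is likely to predict both the 24-hour outcome and whether that score is missing, since a sedated, intubated or transferred patient is harder to score. Missing at random is more credible when such a variable is in the model.

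Without it, a patient who left hospital with a new deficit gets the same imputed risk as one who left intact, given equal arm and baseline profile. At stake are the morbidity rates reported for an endpoint that SAP 6.8 ranks among its most important secondary ones, some power for H2, and, if missingness differs between arms, the relative risk itself.

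**Working it through.** **The plan's own figure.** The only design calculation is for the primary endpoint (SAP 6.5.2: 73% versus 82%, 325 per arm, two-sided 0.05).

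Power = Φ[(0.09·√325 − 1.96·√(2·0.775·0.225)) / √(0.73·0.27 + 0.82·0.18)] = Φ[(1.6225 − 1.1575)/0.5871] = Φ(0.792) = 78.6%.

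This agrees with approximately 80%. It does not bear on H2, for which the documents give no event rate, power or expected missingness.

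**The two imputation models side by side**

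| | Primary endpoint (SAP 6.5.3) | 24-hour morbidity (SAP 6.6.1) |
|---|---|---|
| Fitted by arm | yes | yes |
| Baseline variables | age, sex, two strata, aneurysm size | the same, plus baseline NIHSS |
| Scheduled post-procedure measure | 3-6 month occlusion | discharge NIHSS |
| Used in the model | yes | no |

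**Assumed inputs (none is in the documents).** Let Y be 24-hour morbidity with true rate p, and D be worse NIHSS at discharge.

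- P(D given Y) = 0.80 and P(D given no Y) = 0.05.
- The 24-hour score is missing with probability m1 if D is present and m0 if not.

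**Formula.** Imputation that ignores D reproduces, in expectation, the rate among observed patients:

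estimate = p·a / [p·a + (1−p)·b], where a = 0.80(1−m1) + 0.20(1−m0) and b = 0.05(1−m1) + 0.95(1−m0).

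Baseline covariates are left out here; the second simulation below includes one.

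*m1 = 40%, m0 = 10%:* a = 0.48 + 0.18 = 0.66; b = 0.03 + 0.855 = 0.885.

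- p = 8%: 0.0528/(0.0528 + 0.8142) = 6.1%
- p = 3%: 0.0198/(0.0198 + 0.8585) = 2.3%
- Relative risk: 0.0609/0.0225 = 2.70, against a true 8/3 = 2.67

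*m1 = 60%, m0 = 30%:* a = 0.46; b = 0.685.

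- p = 8%: 0.0368/(0.0368 + 0.6302) = 5.5%
- p = 3%: 0.0138/(0.0138 + 0.6645) = 2.0%

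*m1 = m0:* a = b, so the estimate equals p and there is no bias.

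*Pattern in one arm only* (40%/10% in one arm, 10% throughout in the other, p = 5% in both): 0.05·0.66/(0.05·0.66 + 0.95·0.885) = 0.0330/0.8738 = 3.8%. The other arm is unbiased at 5.0%. The relative risk is 0.0378/0.05 = 0.76 where the truth is 1.00.

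**Simulation** (325 per arm, 30 imputations, Rubin's rules on the log relative risk, draws within arm without and with the discharge indicator):

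| Setting | Without discharge indicator | With it |
|---|---|---|
| 8% vs 3%, 40%/10% missing: rates | 6.1% / 2.3% | 8.0% / 3.1% |
| Same: relative risk | 2.77 | 2.74 |
| No true effect, 40%/10% in both arms: rejection | about 4% | about 4% |
| No true effect, 40%/10% in one arm, 10% in the other: relative risk | 0.74 | 0.99 |
| Same: rejection | about 10% | about 4% |

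Repeated runs gave a power gain of 3 to 6 points when missingness depended on discharge status. The gain was about 0.3 points when it did not.

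**Simulation with a baseline covariate in the imputation model** (true morbidity about 4.6%, discharge deficit in 80% of morbid and 3% of other patients). Patients with a missing score and a discharge deficit were imputed at a risk of 5-6%, against a true 56-58%. Adding the discharge indicator gave 51-54%. With 30% missing among those with a deficit and 10% otherwise, the estimated rate was 3.9% against a true 4.6% without the indicator, and 4.5% against 4.5% with it.

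**Event counts.** With p = 3% and 40%/10% missing, observed events in that arm number 325 × 0.03 × 0.66 = 6.4.

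**The case against.** The strongest reply is that H2 tests a relative risk, and with like missingness in both arms that quantity is almost unchanged (2.77 versus 2.74), with rejection near 4% under no effect. That stands. The illustration also generates missingness from discharge status alone, so adding that status restores missing at random by construction. If missingness follows the 24-hour status itself, some bias would remain after the fix. That stands too, as does the fact that every rate used is assumed.

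A reader might infer that a patient with a recorded procedural stroke is imputed at the overall average of the arm. The SAP does not say that: the model conditions on rupture and neck strata, age, sex, aneurysm size and baseline NIHSS. What is true is that post-procedure status has no influence beyond those variables.

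Discharge is not 24 hours. An early deficit may have resolved, and a later event may be what the discharge score shows. This limits discharge NIHSS to the role of a predictor.

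Severe harm is also seen elsewhere, through deaths within 24 hours, 30-day procedure-related mortality, serious adverse events and mRS. This lowers the stakes but does not correct the reported morbidity rate.

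Finally, if the discharge score is in practice the only early NIHSS, it would be missing together with the outcome and the fix would add nothing. That depends on how the schedule is reconciled.

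**Conclusion.** The omission is real, and at odds with how the same SAP imputes its primary endpoint. Its consequence is conditional:

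- **Missingness unrelated to post-procedure status:** almost no effect.
- **Missingness related to status, alike in both arms:** morbidity rates are understated, by about a quarter under the assumed 40%/10% pattern (8% to 6.1%, 3% to 2.3%), and a few points of power are lost. The relative risk and type I error of H2 are nearly intact.
- **Missingness related to status and different by arm:** the relative risk is biased (1.00 to about 0.74 under the assumed pattern) and rejection under no effect rises to about 10%. This is possible because SAP 3.1.2 leaves investigators unblinded, but nothing in the documents shows that it will occur.

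A reader might infer that H2 as written is an invalid test, or that it must understate harm. The documents support neither. They give no missingness rate or pattern, and understatement requires that worse patients miss the score more often. This is a worthwhile, inexpensive improvement to the imputation model, not a defect shown to change the conclusion of H2.

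**What to change.** In SAP 6.6.1, add discharge NIHSS, as change from baseline or as a worsening indicator, to the fully conditional specification model as an auxiliary variable, still fitted by arm. State that it predicts the 24-hour score and does not replace it.

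Do not add discharge mRS and a procedural serious-adverse-event indicator as a matter of course. With about 6 observed events possible in one arm, the six listed covariates plus three more risk separation. Add them only if event counts support it. Specify a penalised or augmented logistic step in either case.

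State how patients who survive 24 hours but die in hospital without a discharge score are handled.

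Reconcile the visit schedule (protocol 6.1, SAP 3.1.1), which has no baseline or 24-hour NIHSS, with SAP 5.2.1 and 6.6.1, which need both. The value of the added variable depends on this.

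The cost is a short change to the SAP text and minor programming, with a variable already scheduled for collection. The risk is some sparse-data instability. The SAP's purpose statement allows revisions before data lock.

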### **6.6.2 *Survival***

Survival over the full duration of follow-up will be described using Kaplan-Meier curves and compared between the randomization groups using a log-rank test. The hazard ratio and corresponding 95% confidence interval for death in the larger coil group compared to the smaller coil group will be estimated using a Cox proportional hazards model. Patients who withdraw consent or are lost-to-follow up will be censored at the time of study exit. Time to event will be computed as the date of death (or the date of censoring) – randomization date. In cases where the patient dies or is censored the day they are randomized, the time will be coded as 0.5 days.

Causes of death and relatedness to the procedure will also be described by randomization group. The number and proportion of patients that have a procedure related mortality within 30 days post-procedure will be presented by group and group differences will be summarized as a relative risk with the corresponding 95% confidence interval.

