## **7.2 Serious Adverse Events (SAEs) Definition and Reporting Procedures**

### 7.2.1 Definition

1. An SAE will be considered any undesirable sign, symptom, or medical condition which is fatal, life-threatening, requires or prolongs inpatient hospitalization, results in persistent or significant disability/incapacity, constitutes a congenital anomaly or birth defect, is medically significant and which the investigator regards as serious based on appropriate medical judgment. An AE that may not result in death, be life-threatening, or require hospitalization may be considered an SAE when, based upon appropriate medical judgment, may jeopardize the patient and may require medical or surgical intervention to prevent one of the outcomes listed in the definitions of SAEs.

2. The Principal Investigator will report unexpected and serious AEs to the DSMB within 15 working days of notification and all others expeditiously. The DSMB will meet on a semi-annual basis or on ad hoc basis if the PI identifies unusual increases in AEs or unexpected events. The following events require expedited reporting: (1) unexpected serious adverse events (must be both serious and unexpected); (2) peri-procedural death within 30 days of procedure (site PIs may be required to provide additional information on such cases); (3) an increase in the rate of expected SAEs occurring in a center.

3. Events NOT considered to be SAE are hospitalizations for: (1) the routine treatment or monitoring of the studied indication not associated with any deterioration in condition; (2) treatment, which was elective or pre-planned, for a pre-existing condition that is unrelated to the indication under study and did not worsen; (3) admission to a hospital or other institution for general care, not associated with any deterioration in condition; (4) treatment on an emergency, outpatient basis for an event not fulfilling any of the definitions of serious given above and not resulting in hospital admission.

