### 7.2.2 Reporting

1. To ensure patient safety, every SAE, regardless of suspected causality, occurring after the patient has provided informed consent and until the final follow-up visit must be reported to Vanderbilt University Medical Center immediately and within 72 hours of learning of its occurrence.

2. An SAE occurring at a different time point or otherwise considered completely unrelated to a previously reported event should be reported separately as a new event.
3. Information about SAEs will be collected and recorded on the Event Form in the study's electronic database. The investigator must assess the relationship to study intervention and complete the form. This must be completed within 72 hours of discovery for review by the Vanderbilt University Medical Center Study Team.
4. Each re-occurrence, complication, or progression of the original event should be reported as a follow-up to that event regardless of when it occurs. The follow-up information should describe whether the event has resolved or continues and if and how it was treated.

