#### 3.1.2 Randomization and Masking

Patients will be randomly assigned in a 1:1 allocation to receive either larger or smaller coils. Patient randomization will be stratified by clinical site, aneurysm status (recently ruptured versus not), and dome to neck ratio (wide neck versus not). Randomization will be performed centrally through a web-based data collection system that automates the delivery of the randomization assignments.

Investigators will not be blinded to treatment assignment due to the nature of the treatment intervention. Investigators will, however, be blinded to all data from other clinical sites. Clinical outcome assessments will be completed by certified research staff that are not part of the treatment team. All angiograms will be analyzed by a blinded angiogram core laboratory personnel who will be blinded to clinical outcomes. Trial oversight will be provided by an independent Data and Safety Monitoring Board (DSMB).

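### The only 30-day mortality relative risk in SAP 6.6.2 counts deaths called procedure related, an undefined judgement that the protocol gives to unblinded investigators; all-cause 30-day death should be the main contrast

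*Combined protocol and SAP*

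**What the plan says.** SAP section 6.6.2 plans two between-group comparisons of mortality.

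- **All deaths, whole follow-up.** "Survival over the full duration of follow-up will be described using Kaplan-Meier curves and compared between the randomization groups using a log-rank test", with a Cox hazard ratio. This matches the mortality endpoint in SAP 5.2.1, which runs to the final visit.
- **30 days, restricted.** "The number and proportion of patients that have a procedure related mortality within 30 days post-procedure will be presented by group". The arms are then contrasted by a relative risk and its 95% interval. SAP section 5 does not list this 30-day measure as an endpoint.

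The same section adds a description: "Causes of death and relatedness to the procedure will also be described by randomization group". Device is not mentioned.

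The protocol supplies the relatedness data. Under section 7.1.3, every adverse event is recorded with "Its relationship to the procedure, clinical course of the disease, device, or non-procedure". Section 7.2.2 says of serious events: "The investigator must assess the relationship to study intervention and complete the form", and sends the form to the coordinating center's study team for review. SAP 3.1.2 says: "Investigators will not be blinded to treatment assignment due to the nature of the treatment intervention".

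The deaths themselves are captured whatever their cause. Protocol 7.2.2 requires every SAE to be reported irrespective of causality, and 7.2.1 lists "peri-procedural death within 30 days of procedure" among the events needing expedited reporting.

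**The concern.** Whether a death occurred by day 30 is a fact. Whether it was procedure related is a judgement, and here someone who knows which coil size was assigned can make it. The plan protects its other judgement-based outcomes: protocol 6.2.1 has a core lab blinded to arm, and 6.2.2 keeps the treatment team from administering the NIHSS and mRS. Nothing similar is described for attributing deaths. Review by the coordinating center is not described as blinded.

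The category is also open. The eCRF item names procedure, disease course, device and non-procedure. SAP 6.7.1 tabulates relatedness to the investigational agent or the aneurysm. Protocol 3.2 speaks of treatment-related mortality. No rule links any of these to the term used in 6.6.2. Read literally, a death coded to the device falls outside the 30-day contrast, in a trial where coil diameter is what is randomized. So does a death in a recently ruptured patient coded to the disease. For the primary endpoint, SAP 6.5.3 does set a rule for aneurysm-related, unrelated and unknown causes of death; 6.6.2 has none.

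At stake is a published early-safety estimate that could show a difference that is not there, or hide one that is.

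**Working it through.** **Inputs.** 325 patients per arm (SAP 6.5.2). The documents give neither a 30-day death rate nor attribution shares, so there is no planned figure to reproduce. The death counts and shares below are assumptions.

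**Formula.** Let D_L and D_S be all deaths by day 30 in the larger- and smaller-coil arms, and f_L and f_S the shares called procedure related. With equal arms:

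planned RR = (f_L × D_L) / (f_S × D_S) = all-cause RR × (f_L / f_S).

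The distortion factor is therefore f_L / f_S. It is 1 when attribution is the same in both arms, whatever the share. Intervals use the log-RR standard error √(1/a − 1/325 + 1/b − 1/325), where a and b are the two counts.

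**No true difference, 10 deaths per arm** (10/325 = 3.1%). All-cause RR = 10/10 = 1.00 (0.42 to 2.37).

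| Shares, larger vs smaller | Counts | Planned RR (95% CI) |
|---|---|---|
| 60% vs 40% | 6 vs 4 | 1.50 (0.43 to 5.27) |
| 70% vs 30% | 7 vs 3 | 2.33 (about 0.61 to 8.9) |

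For 6 vs 4: SE = √(1/6 + 1/4 − 2/325) = 0.641, and exp(1.96 × 0.641) = 3.51; 1.50/3.51 = 0.43 and 1.50 × 3.51 = 5.27. Reversing the shares gives 0.67 and 0.43.

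**True doubling.**

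| Deaths, larger vs smaller | All-cause RR (95% CI) | Shares | Counts | Planned RR (95% CI) |
|---|---|---|---|---|
| 10 vs 5 | 2.00 (0.69 to 5.79) | 50% vs 100% | 5 vs 5 | 1.00 (0.29 to 3.42) |
| 10 vs 5 | 2.00 (0.69 to 5.79) | 60% vs 80% | 6 vs 4 | 1.50 (0.43 to 5.27) |
| 10 vs 5 | 2.00 (0.69 to 5.79) | 75% vs 75% | 8 vs 4 (rounded) | 2.00 (0.61 to 6.58) |
| 20 vs 10 | 2.00 (0.95 to 4.21) | 50% vs 100% | 10 vs 10 | 1.00 (0.42 to 2.37) |

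The all-cause ratio is the same whatever shares are assumed. The planned ratio moves in either direction when the shares differ by arm; when they are equal, it keeps its value and only loses precision.

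**The case against.** **Early death is compared elsewhere.** This stands. All deaths enter the log-rank and Cox analyses, and 30-day survival can be read off the Kaplan-Meier curves. Deaths within 24 hours count as neurologic morbidity (SAP 6.6.1), and death scores 6 on the mRS (SAP 5.2.2). Neurologic morbidity and the 3-to-6-month mRS are both in the gatekeeping sequence of SAP 6.8. A reader might infer that excluded deaths vanish from the trial, or that no other analysis reflects early mortality. Neither is so. What is missing is an all-cause relative risk at 30 days.

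**The eCRF does not set device deaths apart.** This also stands. A reader might infer from protocol 7.1.3 that device-related deaths form a separate list. The item is a relationship field for all adverse events and does not say that its options exclude one another. Protocol 7.1.2 includes device malfunction among the known risks of coil embolization, which supports reading device deaths as procedural. That is a reason to define the term, since the SAP leaves both readings open.

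**The assessor is inferred.** SAP 6.6.2 names none. Protocol 7.2.2 gives the judgement to the investigator, and SAP 3.1.2 leaves investigators unblinded, so the inference is well grounded.

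**The protocol asks for treatment-related mortality.** Section 3.2 does name it, and dropping the relatedness contrast would leave that outcome without a between-group estimate of deaths attributed to treatment. This is a good reason to keep the planned figure as support. It does not rule out an all-cause contrast: the text following the exclusion criteria in protocol 4.2 counts patients who lack angiography because of death as events for that same outcome, with no relatedness condition on the deaths.

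**The size is assumed and imprecise.** True. The intervals are wide, SAP 6.6.2 plans no p-value for the 30-day measure, and it lies outside the gatekeeping sequence.

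**Conclusion.** The point holds, confined to the 30-day contrast. As written, that relative risk depends on an undefined attribution which, on the protocol's wording, unblinded investigators make, with no blinded adjudication described. Deaths coded to device or disease fall out of it if the term is read literally. The possible distortion is the ratio of attribution shares between arms: a factor of 1.5 at 60% versus 40%, about 2.3 at 70% versus 30%, and 0.5 at 50% versus 100%. These shares, and the 5 to 20 deaths per arm used above, are assumptions.

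The documents do not show that attribution will differ by arm, or in which direction. No formal trial conclusion depends on this estimate. It is a worthwhile, inexpensive correction to a safety figure that will be reported.

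**What to change.** In SAP 6.6.2:

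1. Make all-cause death within 30 days post-procedure, by randomized group, the main 30-day relative risk with 95% confidence interval.
2. Keep the procedure-related relative risk as supportive, and state that it includes deaths attributed to the device.
3. Tabulate 30-day deaths by group across all four eCRF relationship categories.

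No new data are needed, since all deaths are already reportable under protocol 7.2.2, and the SAP allows revision before data lock. The cost is one extra table row and some wording. The downside is that the all-cause count includes deaths from the disease in ruptured patients. These add noise and, if they are unaffected by coil size, pull the ratio toward 1. The supportive figure and the breakdown by category let a reader see how much.
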